13.1 Subject Disposition

The number of subjects screened, randomized, and treated in the study will be presented, together with the number and percentage of subjects who discontinued study drug along with the primary reason for study drug discontinuation, discontinued from the study and the primary reason for study discontinuation.

A tabulation of the number and percentage of subjects included in each analysis set will be provided.

Details regarding randomization assignments, subjects who discontinued study drug and/or study, and subject analysis sets will be reported in by-patient listings.

A separate listing will be provided for the replacement subjects and the subjects replaced, including their demographic and stratification factors.

13.2 Important Protocol Deviations

Prior to the database lock for the primary analysis, the Sponsor or designee medical and statistics personnel will identify and review any deviations from the study protocol. Any protocol deviations that might significantly affect the completeness, accuracy, and/or reliability of the study data or that might significantly affect a subject's rights, safety, or well-being will be classified as important protocol deviations (FDA, ICH, 2013, January).

Tabulation of the number and percentage of subjects with important protocol deviations by center and category within each treatment arm will be presented on the Safety Analysis Set. Categories will be sorted alphabetically, and deviations within each category will be sorted alphabetically. Categories will include:

- Deviations related to study inclusion or exclusion criteria
- Receipt of any prohibited therapies as defined in the protocol
- Significant deviations in study drug administration
- Subjects were not withdrawn after developing withdrawal criteria during the study.

Details for protocol deviations for subjects in the Safety Analysis Set will be provided in the protocol deviations data listing.

13.3 Exposure and Drug Accountability

A summary of exposure and compliance, to be reported on the safety analysis set, will include the total number of tablets taken, compliance (%), total exposure (mg), average daily dose (mg/day), duration of exposure (in weeks), and incidence and duration of dose interruption. These parameters will be calculated as follows:

- Duration of exposure (in weeks) will be calculated as [(date of last dose of study medication – date of first dose of study medication + 1)/7]. The date of first dose of study medication will be collected from the Study Drug Administration CRF page and the date of last dose of study medication will be collected from the End of Treatment CRF page. If there is no date for end of treatment on the End of Treatment CRF page, the last available dose date will be used. See Appendix 4 for a complete set of data handling rules.
- Total number of tablets taken = total number of tablets dispensed – total number of tablets returned. The total number of tablets dispensed and returned will be collected from study drug accountability CRF Page. They are to be collected at study visits and will be summed over the whole study treatment period.
- Total exposure (mg) of IMR-687 = Total number of tablets taken * tablet dose level (100/150/200 mg). IMR-687 will be supplied as 100, 150, or 200 mg white tablets in the study. In the lower dose group (≥ 3.0 to ≤ 4.5 mg/kg), subjects weighing <67 kg will be dispensed 100 mg tablets and those weighing ≥ 67 kg will be dispensed 150 mg tablets. In the higher dose group (4.5 to ≤ 6.7 mg/kg), subjects weighing <67 kg will be dispensed 150 mg tablets and those weighing ≥ 67 kg will be dispensed 200 mg tablets. The dose regimen for all subjects is 2 tablets once daily. The weight

at the baseline will be used to establish the dose level and the same dose level will be used throughout the trial.

- Incidence and duration of dose interruption: as collected from the IP Interruptions CRF page.
- Overall compliance (%) = [(total number of tablets dispensed – total number of tablets returned) / duration of exposure (days)] x 100.
- Average daily dose (mg/day) = total exposure (mg) / duration of therapy (days).

Additional considerations and data handling in exposure and drug accountabilities will be needed for the DMC and IA when some of drug dosing and accountability information is deemed incomplete. See [Appendix 4](#) for a complete set of data handling rules for drug exposure and accountability.

The same tabulation will be generated for the ITT, mITT and PP analysis set if it is not the same as the safety analysis set.

Details of the administration of study drug, including randomized and actual treatment, start date and time of each dose, dose per administration, and date, time, and composition of last meal will be listed on the safety analysis set.

Details of study drug accountability including date dispensed, date returned, amount returned, and compliance per dosing period (in %, as collected directly from CRF), overall compliance (in %, for the whole duration of study drug exposure, as calculated as above) will be listed based on the safety analysis set.

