9. STUDY TREATMENTS

9.1. Study Drug

Study drug (IMR-687 or placebo) is to be taken as 2 tablets orally qd.

IMR-687 will be supplied as 100, 150, or 200 mg white tablets. To optimize dosing, 60 kg will be used as the body weight gate for the administered tablet strength. Subjects in the lower dose group weighing <60 kg will be dispensed 100 mg tablets, and those weighing \geq 60 kg will be dispensed 150 mg tablets. Subjects in the higher dose group weighing <60 kg will be dispensed 150 mg tablets and those weighing \geq 60 kg will be dispensed 200 mg tablets. The different doses of IMR-687 are visually identical in tablet form.

Placebo will be supplied as white tablets containing matrix absent IMR-687. The placebo tablets are visually identical to the IMR-687 tablets.

Subjects will be directed to take study drug (either IMR-687 or placebo) with food, but if a subject does not do so, it will not be considered a protocol deviation.

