6.0 Introduction

This SAP should be read in conjunction with the study protocol and case report form (CRF). Any further changes to the protocol or CRF may necessitate updates to the SAP prior to database lock. If the SAP and the final protocol are different, the SAP prevails.

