8.0 Study Design

This is a Phase 2b, randomized, double-blind, placebo-controlled, multicenter study of subjects aged 18 to 65 years with sickle cell disease (SCD; homozygous sickle hemoglobin [HbSS], sickle- β^0 [HbS β^0] thalassemia, or sickle- β^+ [HbS β^+] thalassemia) to evaluate the safety and efficacy of the phosphodiesterase type 9 inhibitor, IMR-687, administered once daily (QD) for 52 weeks. This study will enroll approximately 99 subjects with SCD. This study consists of a screening period (up to 4 weeks), a double-blind treatment period (52 weeks), and a safety follow-up period (4 weeks).

The study schematic is provided in [Figure 1](#) below, and the schedule of assessments is provided in [Appendix 3](#) of this document.

Subjects will receive either IMR-687 (lower dose or higher dose) or placebo in a blinded fashion. IMR-687 will be supplied as 100, 150, or 200 mg white tablets. Placebo and the different doses of IMR-687 are visually identical. Subjects will be advised to take 2 tablets orally, once daily (QD). Prior to the Protocol version 4.0, lower dose was defined as an exposure of ≥ 3.0 to ≤ 4.5 mg/kg, subjects in the lower dose group weighing <67 kg will be dispensed 100 mg tablets and those weighing ≥ 67 kg will be dispensed 150 mg tablets. Higher dose was defined as an exposure of >4.5 to ≤ 6.7 mg/kg, subjects in the higher dose group weighing <67 kg will be dispensed 150 mg tablets and those weighing ≥ 67 kg will be dispensed 200 mg tablets. In Protocol version 4.0 and later, lower dose was defined as an exposure of ≥ 3.4 to ≤ 5.0 mg/kg, subjects in the lower dose group weighing <60 kg will be dispensed 100 mg tablets and those weighing ≥ 60 kg will be dispensed 150 mg tablets. Higher dose was defined as an exposure of >5.0 to ≤ 6.7 mg/kg, subjects in the higher dose group weighing <60 kg will be dispensed 150 mg tablets and those weighing ≥ 60 kg will be dispensed 200 mg tablets.

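### SAP 13.3 leaves the two-tablet regimen out of overall compliance (full adherence reads 200%) and sets tablet strength by the 67 kg weight gate alone, understating dose for some active-arm subjects.

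*SAP*

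**What the plan says.** SAP 13.3 takes tablets taken as those dispensed minus those returned. Overall compliance divides that count by calendar days only (the formula runs "total number of tablets returned) / duration of exposure (days") and multiplies by 100. The same section states: "The dose regimen for all subjects is 2 tablets once daily". The by-subject listing repeats the quantity: "overall compliance (in %, for the whole duration of study drug exposure, as calculated as above").

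Total exposure in mg is tablets taken times tablet strength, and average daily dose is that total divided by days. For the strength, 13.3 gives one weight gate, 67 kg, with the older mg/kg ranges and no reference to protocol version. It adds that the weight "at the baseline will be used to establish the dose level and the same dose level will be used throughout the trial".

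SAP 8.0 has two gates. The 67 kg rule is introduced by "Prior to the Protocol version 4.0, lower dose was defined as an exposure of" the older range, and the 60 kg rule by "In Protocol version 4.0 and later, lower dose was defined as an exposure of" the newer range. Protocol 9.1 has only the second: "To optimize dosing, 60 kg will be used as the body weight gate for the administered tablet strength".

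SAP 13.3 refers the reader to Appendix 4 for the full data handling rules. Appendix 4 defines duration of exposure as last dose date minus first dose date plus 1. It has no compliance rule and no tablet-strength rule.

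**The concern.** The compliance formula has no tablets-per-day term, so it reports tablets per day as a percentage. It cannot return 100% for a subject who follows the regimen. A subject who took 40% of the tablets would read 80%, which is the threshold Protocol 9.5 uses for compliance between visits.

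The weight rule is a different kind of error. Randomization ran from August 2020 to August 2021 (SAP 8.1.1) and Version 4.0 is dated 08 Apr 2021 (SAP 13.5.9), so enrolment spans the change of gate. A rule with one gate cannot describe both periods. Where the two gates disagree, 13.3 credits the weaker tablet.

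At stake are the overall compliance, total exposure and average daily dose summaries. They are produced for the safety set, and for ITT, mITT and PP where these differ from it. Exposure is planned at both the interim and the final analysis (SAP Table 4). In a trial with two dose arms, the mean daily dose per arm is a basic description of the treatment delivered.

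**Working it through.** The SAP states a formula but no compliance result, so there is no published figure to reproduce. The check puts known cases through the rules as written.

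**Inputs**
- Regimen: 2 tablets per day (SAP 13.3, Protocol 9.1).
- Treatment period: 52 weeks = 364 days (Protocol synopsis).
- Tablet strength below / at or above the gate: lower dose 100 / 150 mg, higher dose 150 / 200 mg.
- Gate: 67 kg in SAP 13.3; 60 kg from Version 4.0 in SAP 8.0 and in Protocol 9.1.

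**Compliance**

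Tablets at full adherence: 2 x 364 = 728.

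| True adherence | Tablets | As written: tablets / 364 x 100 | With regimen: tablets / (2 x 364) x 100 |
|---|---|---|---|
| 100% | 728 | 200% | 100% |
| 80% | 582.4 | 160% | 80% |
| 50% | 364 | 100% | 50% |
| 40% | 291.2 | 80% | 40% |

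Days cancel, so the factor of 2 is the same at any duration. Total exposure and average daily dose do not share this fault, because the tablet count already contains the two tablets per day.

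**Dose**

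Below 60 kg and at or above 67 kg the two gates give the same strength. They differ only from 60 to <67 kg. For a subject in that band dosed under the 60 kg gate, at full adherence over 364 days:

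| Arm | Credited by 13.3 | Dispensed per SAP 8.0 | Difference |
|---|---|---|---|
| Lower dose | 728 x 100 = 72,800 mg (200 mg/day) | 728 x 150 = 109,200 mg (300 mg/day) | -36,400 mg (-33.3%) |
| Higher dose | 728 x 150 = 109,200 mg (300 mg/day) | 728 x 200 = 145,600 mg (400 mg/day) | -36,400 mg (-25.0%) |

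Each affected subject is understated by 100 mg/day, so an arm's mean shifts by the affected share x 100 mg/day. The share is not in the documents. Assumed shares of 10%, 20% and 30% give 10, 20 and 30 mg/day.

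**The case against.** The strongest points on the other side are these.

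- **Permitted reductions and holds.** Protocol Table 2 allows a one-tablet reduction for up to 14 days and holds of up to 7 days or longer. Measured against tablets prescribed, the overstatement is then slightly under 2. With 14 tablets legitimately omitted, 714 / 364 = 196.2% where full compliance with the prescription is 100%. The suggested denominator would read 714 / 728 = 98.1%. This is fair: the SAP should state which convention it intends. It does not rescue the formula, which is still close to double.
- **Section 8.0 already has the right history.** A careful programmer could use it, and could read the weight text in 13.3 as description. But 13.3 says how the dose level is established, and it is the section that defines the derivation. The precedence clause ("If the SAP and the final protocol are different, the SAP prevails") cannot decide between two SAP sections, and it stops Protocol 9.1 from overriding 13.3.
- **The data may expose the error.** SAP 13.3 plans a listing of dose per administration, though it does not say whether every dose or only clinic doses are covered. A 200% compliance figure would be noticed at the first table review. The dose error is less visible, since 200 and 300 mg/day are legitimate values in the lower and higher dose arms respectively.
- **The outputs are descriptive.** This stands in full. Per-period compliance is taken from the CRF, so nothing in the documents ties the 80% deviation rule to this formula. No analysis set or efficacy test is defined by these quantities.
- **The 10% to 30% range has no source.** It is an illustration. The true share could be lower, since sites had to await approvals before applying an amendment (Protocol 15.1.1).

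**Conclusion.** Both parts are wrong as written. Against the two-tablet regimen, overall compliance is overstated by a factor of exactly 2 for every subject in every arm. Because the factor is constant, the correct value can be recovered from tablets taken and duration.

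The dose error is confined to active-arm subjects of 60 to <67 kg dosed under the 60 kg gate, and arises if the baseline-weight rule is programmed as stated. It is -33% (lower dose) or -25% (higher dose) per affected subject. It cannot be undone from the summary table, because only an unidentified subset is affected. Placebo subjects, other weights, and subjects dosed under the earlier gate who kept their strength are unaffected. The effect on arm means depends on a share that the documents do not give.

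This should be corrected, but it does not threaten the efficacy conclusions. Nothing here bears on which gate or dose is clinically appropriate.

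**What to change.** 1. Define overall compliance (%) as tablets taken / (2 x duration of exposure in days) x 100. State whether protocol-permitted reductions and holds count against compliance or are removed from the denominator.
2. Compute total exposure (mg), and hence average daily dose, from the tablet strength actually dispensed. If that is not in the analysis data, use a weight rule specific to the protocol version under which the subject was dosed.
3. Reconcile the weight gates and mg/kg ranges in SAP 13.3 with SAP 8.0 and Protocol 9.1.

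The cost is one formula and one sentence in the SAP. For item 2, SAP 13.3 names only tablet counts on the accountability page, so strength would come from the bottle code (Protocol 10.2) or possibly from the planned dose-per-administration data. The version-specific rule needs only each subject's protocol version at dosing, but the documents do not say whether subjects already enrolled changed strength at Version 4.0. If any did, one strength per subject is not enough, and dispensed strength is the safer source.

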13.4 Demographic and Baseline Characteristics

Demographics, baseline and disease characteristics will be summarized for all analysis sets. The following are included:

- Age (years) –as a continuous variable
- Sex (Female, Male)
- Ethnicity (Categories as collected from CRF)
- Race (Categories as collected from CRF)
- Region (North America/Europe, Africa/Middle East)
- Height (cm)
- Weight (kg)
- BMI (kg/m²)
- Diagnosis Type (HbSS, HbSB0 thalassemia, HbSB+ thalassemia)
- Baseline HU Use (as collected from IRT)
- Actual Baseline HU Use (as collected from Prior and Concomitant Medications CRF)
- Number of VOCs in the past 12 months (in categories of 1, 2-4, 5-7, 8-12 and as a continuous variable)
- The number of hospitalizations for VOCs in the past 12 months ((in categories of 1, 2, 3, ≥ 4 and as a continuous variable)
- Baseline HbF - as a continuous variable

- Baseline Hb - as a continuous variable

The median value of Age and Baseline HbF/Hb will be determined by the median in the ITT analysis set and displayed as a numeric value in tabulations.

13.4.1 Medical and Surgical history

Medical and Surgical history will be coded using Medical Dictionary for Regulatory Activities (MedDRA, version 23.0 or higher) and will be summarized for the safety analysis set, by treatment group and overall, using System Organ Class (SOC) and MedDRA preferred term (PT). The table will include the number and percentage of subjects and will be sorted alphabetically by SOC and in decreasing frequency by PT and then alphabetically for ties (based on the total count in the analysis set). A subject will only be counted once within a class.

A by-patient listing will show medical and surgical history generated on the safety analysis set.

13.4.2 Prior and Concomitant Medications

Concomitant medications are medications ongoing at the time of the first dose of study drug or medications that started after first dose and within 30 days of the last dose of study drug. Any medication that was used at any time prior to the date of first study drug is a Prior Medication.

Medications will be captured on the Prior and Concomitant Medications CRF and coded using the WHO Drug dictionary (WHODDE 01MAR2020 or later version).

Prior medication and concomitant medications will be summarized separately by Anatomical Therapeutic Chemical (ATC) Level 2 and preferred terms for the safety analysis set. If ATC-2 is missing, the next non-missing level will be used. The summary will be sorted by ATC class alphabetically, then by descending frequency for preferred term in the pooled IMR-687 dose column and then alphabetically for ties. A patient will only be counted once within each ATC class and within each preferred name.

Medications related to sickle cell disease can be identified in the Prior and Concomitant Medications CRF when the Primary Reason Medication = Disease Under Study. Prior medication and concomitant medications related to sickle cell disease will be summarized separately, in a similar manner as for the general prior and concomitant medications.

In addition, opioids and pain medications will be identified via Standardized Drug Groupings (SDGs) and the concomitant use of opioids and the concomitant use of pain medications will be summarized in a similar manner as for concomitant medications.

All prior and concomitant medications data will be presented in a listing for the safety analysis set.

13.4.3 Concomitant Procedures

The number and percentage of subjects having concomitant procedures will be tabulated for the safety analysis set by treatment group using MedDRA (version 23.0 or later). Procedures will be classified by SOC, then by PT. Subjects will only be counted once within each SOC and PT. The SOCs and PTs will be sorted in descending frequency, using the numbers in the higher dose IMR-687 treatment arm, and then alphabetically in the event of any ties.

All concomitant procedures data will be presented in a listing based on the Safety Analysis Set.

13.5 Endpoint Analyses

13.5.1 Summary of Analyses

Primary efficacy endpoint, safety endpoints, secondary efficacy endpoints, and corresponding analysis methods are summarized in [Table 7](#) below. Exploratory analyses are detailed in [Section 13.5.5](#).

Table 7 Summary of Efficacy and Safety Analyses

| Endpoints | Analysis Time Points | Analysis Methods | Analysis Set | Time Point for analysis |
|--|---|--|--|-------------------------|
| Primary Efficacy • Annualized rate of VOCs | NA | Comparison of median differences among treatment groups using Stratified Wilcoxon rank-sum tests, with stratification factors of region and HU use. The van Elteren test may be used for the evaluation of treatment difference across strata. P-values for each active group (including pooled IMR-687) vs. placebo | ITT as primary analysis set, mITT, PP as sensitivity | IA, FA |
| Safety | NA | Descriptive statistics | Safety | IA, FA |
| Secondary Efficacy | | | | |
| • Time to first VOC • Time to second VOC | NA | Stratified log rank test, and stratified Cox regression model. p-values from a stratified log rank test and hazard ratios (with 95% CIs) estimated from a stratified Cox regression model with treatment arm and stratification factors of region and HU use as covariates will be provided for comparison of each active group (including pooled IMR-687) vs. placebo | ITT as primary analysis set, mITT, PP as sensitivity | IA*, FA |
| • Annualized rate of VOC-related hospitalizations • Annualized rate of days hospitalized for VOC-related hospitalizations | NA | Stratified Wilcoxon rank-sum tests, with stratification factors of region and HU use. P-values for each active group (including pooled IMR-687) vs. placebo | ITT as primary analysis set, mITT, PP as sensitivity | IA*, FA |
| • Proportion of VOC-free subjects • HbF responder rate at Week 24 and Week 52 • Hb responder rate at Week 24 and Week 52 | NA | Stratified CMH test adjusted for stratification factors of region and HU use. | ITT as primary analysis set, mITT, PP as sensitivity | IA*, FA |
| Change from baseline at Week 24 and Week 52 • HbF (%) • F-cells (%) • Total Hb (g/dL) | Baseline to Week 24 and Baseline to Week 52 | MMRM analysis with fixed effects for treatment, visit, and treatment-by-visit interaction, and baseline value, region, and HU use as covariates. Mean (95% CI), Mean difference (95% CI), and p-value will be provided (IA/FA). Both change from baseline and percentage change from baseline will be analyzed (IA/ FA). | ITT as primary analysis set, mITT, PP as sensitivity | FA |
| Change from baseline at Week 24 and Week 52 • Biomarkers of RBC Hemolysis (% and | Baseline to Week 24, | MMRM analysis with fixed effects for treatment, visit, and treatment-by-visit interaction, and baseline value, region, and HU use as covariates. Mean (95% CI), Mean difference (95% CI), and p- | ITT, mITT | FA |

| Endpoints | Analysis Time Points | Analysis Methods | Analysis Set | Time Point for analysis |
|---|--|--|--------------|-------------------------|
| absolute reticulocytes, unconjugated [indirect] bilirubin and LDH) 
 • Biomarkers of adhesion such as Soluble E-sel, P-sel, ICAM-1, and VCAM-1 • Biomarkers of inflammation such as hsCRP and MPO • Biomarkers of cardiac stress such as NT-proBNP • RBC indices, such as MCV | Baseline to Week 52 | value will be provided. Both change from baseline and percentage change from baseline will be analyzed. | | |
| Change from baseline at Week 24 and Week 52 
 • Each measured subdomain of Adult Sickle Cell Quality of Life Measurement Information System (ASCQ-Me) questionnaire • Total preference score and individual domain scores of the Patient-Reported Outcomes Measurements Information System – Preference (PROMIS 29 + 2 Profile v2.1 [PROPr]) questionnaire • Overall scores of the Sickle Cell Self-Efficacy Scale (SCSES) | Baseline to Week 24, Baseline to Week 52 | ANCOVA analysis with fixed effects for treatment, and baseline value, region, and HU use as covariates. Mean (95% CI), Mean difference (95% CI), and p-value will be provided. | ITT | FA |

* Key secondary and other secondary endpoints will be tested in hierarchical order through a gatekeeping procedure.

